7.2 Medical History

Medical history data will be summarized and presented using body systems and conditions/diagnoses as captured on the eCRF. The body systems will be presented in alphabetical order and the conditions/diagnoses will be presented in alphabetical order within each body system. The number and percentage of subjects with a particular condition/diagnosis will be summarized for all treated subjects. Subjects reporting more than one condition/diagnosis within a body system will be counted only once for that body system.

7.3 Prior, Concomitant and Post-Treatment Medications

A prior medication is defined as any medication taken prior to the date of the first dose of study drug (GLE/PIB). A concomitant medication is defined as any medication that started prior to the date of the first dose of study drug and continued to be taken on or after the first dose of study drug or any medication that started on or after the date of the first dose of study drug, but not after the date of the last dose of study drug. A post-treatment medication for the treatment of HCV is defined as any medication taken on or after the last dose of study drug and entered as "Post-treatment HCV medications" on the eCRF.

The number and percentage of subjects taking prior medications, concomitant medications, and post-treatment HCV medications will be summarized by generic drug name based on the WHO Drug Dictionary. The prior HCV medications taken by treatment experienced subjects and collected on the "Last Prior HCV Therapy" and "Second to Last Prior HCV Therapy" eCRFs will be summarized separately from other prior medications, and will not be included in the summary of all prior and concomitant medication.

8.0 Patient Disposition

The number and percentage of subjects who screen failed for any reason will be summarized for subjects who screen failed and by each screen fail reason.

8.1 Disposition of Safety Population

The number of subjects in each of the following categories will be by investigator for each age group and overall.

- Enrolled subjects;
- Subjects who took at least one dose of study drug;
- Subjects who completed study drug;
- Subjects who prematurely discontinued study drug;
- Subjects who completed the study;
- Subjects who prematurely discontinued from the study;
- Subjects ongoing in the Post-Treatment Period (if applicable at the time of analysis).

The number and percentage of subjects who discontinued study drug will be summarized by reason (all reasons) and by primary reason (per eCRF) for each age group and overall. Similar summaries will be provided for discontinuations from the study.

The number and percentage of subjects with reported study drug interruptions will be summarized by age group and overall. Reasons for study drug interruptions will be presented in the CSR listings.

9.0 Study Drug Exposure and Compliance

Exposure and compliance will be summarized on the ITT population by age group and overall.

9.1 Exposure

The duration of exposure to study drug will be summarized by assigned treatment duration for each age group and for all subjects. Duration of exposure is defined for each subject as the last study drug dose date minus the first study drug dose date plus 1 day.

Descriptive statistics (mean, standard deviation, median, minimum, and maximum) will be presented for exposure during the treatment period.

Study drug duration will be summarized with frequencies and percentages using the following categories:

- 1 to 30 days
- 31 to 60 days
- 61 to 75 days
- 76 to 90 days
- 91 to 105 days
- > 105 days

In addition, the number and percentage of subjects with study drug duration of ≥ 52 days for subjects assigned to 8 weeks, ≥ 77 days for subjects assigned to 12 weeks and ≥ 103 days for subjects assigned to 16 weeks will be summarized by age group and overall.

9.2 Compliance

For the adult formulation, the GLE/PIB tablet, tablet is the dose unit for drug accountability. For the pediatric formulation, bottle/sachet is the dose unit for drug accountability and the return status for each dose unit is recorded as either full/sealed, empty, or unsealed but not empty separately for glecaprevir and pibrentasvir or for glecaprevir and pibrentasvir combined if mixed together. A bottle/sachet is considered to be taken only if the return status is empty.

At each visit (starting with the Week 4 visit) during the Treatment Period, the total number of dose units dispensed and returned is recorded. The compliance for each type of dose unit during the treatment period will be calculated as the percentage of dose units taken relative to the total dose units expected to be taken. The total number of dose units expected to be taken will be equal to the total number of dose units that should have been taken per the protocol for the duration that the subject was in the Treatment Period (date of last dose of study drug – date of first dose of study drug + 1). Study drug interruptions recorded on the eCRF will not be subtracted from the duration.

A subject is considered to be compliant if the percentage is between 80% and 120%. Compliance will be calculated for each subject and each type of dose unit and summarized separately with the mean, median, standard deviation, minimum, and maximum for each type of dose unit by age group and overall. A listing of compliance for each subject will be provided. The percentage of compliant subjects will be summarized for each study drug by age group and overall, based on data as observed.

10.0 Efficacy Analysis

10.1 General Considerations

General Considerations

All efficacy analyses will be performed on the ITT population, unless otherwise specified.

Missing data will be imputed as described in Section 6.3 for analyses of the HCV RNA endpoints of SVR.

Plasma HCV RNA levels will be determined for each sample collected by the central laboratory using the Roche COBAS® AmpliPrep/COBAS® TaqMan® HCV Quantitative Test, v2.0. The lower limit of detection (LLOD) and lower limit of quantification (LLOQ) for this assay (regardless of genotype) are both 15 IU/mL.

HCV RNA results that are detectable but not quantifiable are reported as "< 15 IU/ML HCV RNA DETECTED" and those that are undetectable are reported as "HCV RNA NOT DETECTED" in the database.

The notation "HCV RNA < LLOQ" is used to represent all HCV RNA values < 15 IU/mL, including values reported as "HCV RNA NOT DETECTED" or "< 15 IU/ML HCV RNA DETECTED." HCV RNA \geq LLOQ are all quantifiable values of 15 IU/mL or greater.

Definitions for Efficacy Endpoints

A confirmed quantifiable value during treatment is defined as any two consecutive HCV RNA measurements \geq LLOQ (or 100 IU/mL for **Breakthrough**), either both during treatment or at the final treatment measurement and the next consecutive post-treatment measurement. A confirmed quantifiable post-treatment value is defined as any two consecutive post-treatment HCV RNA measurements \geq LLOQ.

Breakthrough = confirmed HCV RNA \geq 100 IU/mL after HCV RNA < LLOQ during the Treatment Period; or confirmed increase from nadir in HCV RNA (two consecutive HCV RNA measurements $> 1 \log_{10}$ IU/mL above nadir) at any time point during the Treatment Period. A single breakthrough value (\geq 100 IU/mL or $> 1 \log_{10}$ above nadir) followed by lost to follow-up also will be considered a breakthrough (i.e., will not require confirmation).

EOT failure = HCV RNA \geq LLOQ at end of treatment with at least 6 weeks of treatment, where the HCV RNA value must be collected on or after Study Drug Day 36 and study drug duration \geq 36 days.

On-treatment virologic failure = **Breakthrough** or **EOT failure**; if a subject meets both definitions of Breakthrough and EOT failure, he or she will be categorized as Breakthrough only.

SVR₄ = HCV RNA $<$ LLOQ in the SVR₄ window (4 weeks after the last actual dose of study drug) without any confirmed quantifiable (\geq LLOQ) post-treatment value before or during that SVR window.

SVR₁₂ = HCV RNA $<$ LLOQ in the SVR₁₂ window (12 weeks after the last actual dose of study drug) without any confirmed quantifiable (\geq LLOQ) post-treatment value before or during that SVR window.

SVR₂₄ = HCV RNA $<$ LLOQ in the SVR₂₄ window (24 weeks after the last actual dose of study drug) without any confirmed quantifiable (\geq LLOQ) post-treatment value before or during that SVR window.

Relapse₁₂ = confirmed HCV RNA \geq LLOQ between end of treatment and 12 weeks after last actual dose of active study drug (up to and including the SVR₁₂ window) for a subject with HCV RNA $<$ LLOQ at Final Treatment Visit who completed treatment excluding reinfection as described below.

Relapse₂₄ = confirmed HCV RNA \geq LLOQ within the SVR₂₄ window for a subject who achieved SVR₁₂ and has HCV RNA data available in the SVR₂₄ window, excluding reinfection.

Relapse_{overall} = confirmed HCV RNA \geq LLOQ between end of treatment and up to and including the last HCV RNA measurement collected in the PT Period for a subject with HCV RNA $<$ LLOQ at Final Treatment Visit who completed treatment excluding reinfection.

Virologic failure = On-treatment virologic failure or Relapse_{overall}.

Only subjects who have at least one post-treatment HCV RNA value will be included in analyses of relapse. For the analysis of relapse, completion of treatment is defined as a study drug duration of 52 days or greater for subjects assigned to 8 weeks of treatment, 77 days or greater for subjects assigned to 12 weeks of treatment, and 103 days or greater for subjects assigned to 16 weeks of treatment. If the last available post-treatment value is \geq LLOQ, then the subject will be considered a relapse (i.e., will not require confirmation).

HCV reinfection is defined as confirmed HCV RNA \geq LLOQ after the end of active treatment in a subject who had HCV RNA $<$ LLOQ at Final Treatment Visit, along with the post-treatment detection of a different HCV genotype, subtype, or clade compared with baseline, as determined by phylogenetic analysis of the NS3 or NS5A, and/or NS5B gene sequences. Reinfection in the case of the same HCV subtype is defined as a clade switch, as indicated by the lack of clustering between the baseline and post-treatment sequences by phylogenetic analysis. If phylogenetic analysis is not possible due to technical difficulties, HCV reinfection may be determined with a confirmed HCV genotype or subgenotype switch by the Versant HCV Genotype Inno-LiPA Assay v2.0 or Sanger assay.

Post-treatment relapse is defined as described earlier (**Relapse₁₂**, **Relapse₂₄**, **Relapse_{overall}**), and no genotype, subtype, or clade switch compared with baseline as determined by phylogenetic analysis of the NS3 or NS5A gene sequences. If phylogenetic analysis is not possible due to technical difficulties, the subject will be defined as having a post-treatment relapse unless an HCV genotype or subtype switch is confirmed by the Versant HCV Genotype Inno-LiPA Assay v2.0 or Sanger assay.

Reasons for SVR₁₂ Non-Response

Subjects who do not achieve SVR₁₂ (SVR₁₂ non-responders) will be categorized as having:

1. On-treatment virologic failure (see **On-treatment virologic failure** definition);

2. HCV reinfection (see definition described earlier);
3. Relapse₁₂;
4. Prematurely discontinued study drug with no on-treatment virologic failure (defined as any SVR₁₂ non-responder who prematurely discontinued study drug [study drug duration < 52 days for subjects assigned to 8 weeks of treatment, < 77 days for subjects assigned to 12 weeks of treatment, and < 103 days for subjects assigned to 16 weeks of treatment] and did not meet the **On-treatment virologic failure or reinfection** definitions);
5. Missing follow-up data in the SVR₁₂ window (defined as any subject who completed study drug without data in the SVR₁₂ window after applying the imputation rules and not meeting the definitions of [1], [2], [3], or [4]);
6. Other (defined as any SVR₁₂ non-responder not meeting the definitions of [1] – [5]).

Reasons for SVR₂₄ Non-Response

Subjects who do not achieve SVR₂₄ (SVR₂₄ non-responders) will be categorized as having:

1. On-treatment virologic failure (see **On-treatment virologic failure** definition);
2. HCV reinfection;
3. Relapse₁₂
4. Relapsed₂₄;
5. Prematurely discontinued study drug with no on-treatment virologic failure (defined as any SVR₂₄ non-responder who prematurely discontinued study drug [study drug duration < 52 days for subjects assigned to 8 weeks of treatment, < 77 days for subjects assigned to 12 weeks of treatment, and < 103 days for subjects assigned to 16 weeks of treatment] and did not meet the **On-treatment virologic failure, Relapse₁₂, or Relapsed₂₄** definitions);

6. Missing follow-up data in the SVR₂₄ window (defined as any subject who completed study drug without data in the SVR₂₄ window after applying the imputation rules and not meeting the definitions of [1], [2], [3], [4], or [5]);
7. Other (defined as any SVR₂₄ non-responder not meeting the definitions of [1] – [6]).

For the reasons for SVR₁₂ and SVR₂₄ nonresponse defined above, subjects are only to be counted in 1 category. Specifically, subjects who were SVR₁₂ or SVR₂₄ nonresponders meeting the definition of HCV reinfection will be counted in the reinfection category regardless of whether they meet the definition of prematurely discontinued study drug, relapse₁₂ or relapse₂₄.

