### **8.1.2.2 Secondary Endpoints**

The secondary endpoints are:

1.  $C_{max}$  and clearance of GLE and PIB at Week 2;
2. The percentage of subjects with SVR12 by age group and overall;
3. The percentage of subjects with on-treatment virologic failure (i.e., breakthrough, defined as confirmed increase of  $> 1 \log_{10}$  IU/mL above nadir during treatment or confirmed HCV RNA  $\geq 100$  IU/mL after HCV RNA  $< \text{LLOQ}$  during treatment, or HCV RNA  $\geq \text{LLOQ}$  at the end of treatment with at least 6 weeks of treatment) by age group and overall;
4. The percentage of subjects with post-treatment relapse (defined as confirmed HCV RNA  $\geq \text{LLOQ}$  between end of treatment and 12 weeks after the last dose of study drug among subjects who completed treatment as planned with HCV RNA  $< \text{LLOQ}$  at the end of treatment; excluding subjects who have been shown to be re-infected) by age group and overall;
5. The percentage of subjects with new HCV infection (i.e., re-infection) at any time up to the last visit by age group and overall;
6. Assessment of palatability/acceptability of the pediatric formulation by age group and overall.

The number and percentage of subjects achieving SVR12 will be summarized along with a two-sided 95% confidence interval using the normal approximation to the binomial distribution, unless the number of subjects who fail to achieve SVR12 is less than 5, where the Wilson's score method will be used for the confidence interval instead.

In addition, a summary of reason for SVR12 non-response (e.g., on-treatment virologic failure, relapse, reinfection, other) will be provided for each age group.

For the analysis of on-treatment virologic failure, relapse, and re-infection, the number and percentage of subjects will be summarized along with a two-sided 95% confidence interval using Wilson's score method.

For the analysis of post-treatment HCV virologic relapse, completion of treatment is defined as any subject with study drug duration of 52 days, 77 days, and 103 days or greater for subjects allocated to treatment durations of 8 weeks, 12, and 16 weeks, respectively.

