5.1.2 Modified Intention-to-Treat (mITT) Population

Sensitivity analyses of SVR₁₂ as described in Section 10.5 will be performed on the ITT population modified to exclude subjects who did not achieve SVR₁₂ for reasons other than virologic failure (mITT-VF).

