6.1.2 Study Days

Study days are calculated for each time point relative to the first dose of study drug. Study days are negative values when the time point of interest is prior to the first study drug dose day. Study days are positive values when the time point of interest is after the first study drug dose day. There is no Study Day 0. Study Day 1 is the day of the first dose of study drug.

Study Drug End Days (Days Relative to the Last Dose of Study Drug)

Study drug end days are calculated for each time point relative to the last dose of study drug. The last day of study drug dosing is defined as Study Drug End Day 0. Days before it have negative study drug end days and days after it have positive study drug end days.

Final Treatment Value

The final treatment value is defined as the last non-missing measurement collected after Study Day 1 and on or before Study Drug End Day 2.

Final Post-Treatment Value

The final post-treatment value for each subject is the last non-missing measurement collected after Study Drug End Day 2 and on or before Study Drug End Day 1,999.

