b. For 12-week treatment only.

c. For 16-week treatment only.

d. The last value within the window will be used to define the Final Treatment Visit value. The upper bound of this Final window is Study Drug End Day ≤ 2.

Note: Data must also have Study Drug End Day ≤ 2 for all windows. The result closest to the scheduled time point will be used.

Table 4. Analysis Time Windows for HCV RNA and Resistance Endpoints (Post-Treatment Period)

Scheduled Visit ^a	Nominal Day (Study Drug End Day)	Time Window (Study Drug End Day Range)
Post-Treatment Week 4	28	3 to 56
Post-Treatment Week 12	84	57 to 126
Post-Treatment Week 24	168	127 to 210
Post-Treatment Week 36	252	211 to 294
Post-Treatment Week 48	336	295 to 504
Post-Treatment Week 96	672	505 to 840
Post-Treatment Week 144	1,008	841 to 1,999
SVR ₄ ^b	28	3 to 56
SVR ₁₂ ^b	84	57 to 126
SVR ₂₄ ^b	168	127 to 210

a. Post-Treatment Visits are applicable to subjects who received at least one dose of study drug.

b. For SVR windows, the last value in the window will be used.

Note: The result closest to the scheduled time point will be used, except for SVR₄, SVR₁₂, and SVR₂₄. Data must also have Study Drug End Day > 2 for all windows. Study Drug End Day 0 is defined as the day of the last dose of study drug.

Table 5. Laboratory Data, Vital Sign Measurements, Growth and Development Endpoints (Except Growth Rate) Visit Windows (Post-Treatment Period)

Scheduled Time	Nominal Day (Study Drug End Day)	Time Window (Study Drug End Days Range)
Post-Treatment Week 4	28	3 to 42
Post-Treatment Week 12	84	71 to 126
Post-Treatment Week 24	168	127 to 210
Post-Treatment Week 36	252	211 to 294
Post-Treatment Week 48	336	295 to 504
Post-Treatment Week 96	672	505 to 840
Post-Treatment Week 144	1,008	841 to 1,999
Final Post-Treatment Visit ^a	> 2 days after the last dose of study drug	

a. The last value within the Post-Treatment Period window will be used to define the final post-treatment value. The lower bound of this Final window is Study Drug End Day 3.

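### SAP 10.1: an 8-week completer with a late end-of-treatment sample and a quantifiable Week 4 value cannot be scored as a relapse

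*SAP*

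**What the plan says.** SAP 10.1 allows Relapse12, and in parallel terms Relapse_overall, only "for a subject with HCV RNA $<$ LLOQ at Final Treatment Visit who completed treatment excluding reinfection as described below". The re-infection definition in the same section carries the same Final Treatment Visit condition. Virologic failure is then on-treatment virologic failure or Relapse_overall.

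SAP 6.1.2 takes as the final treatment value "the last non-missing measurement collected after Study Day 1 and on or before Study Drug End Day 2". The footnote to Table 3 in SAP 6.2 agrees: "The last value within the window will be used to define the Final Treatment Visit value". Neither text requires the value to be near the end of treatment. Under SAP Table 4, HCV RNA from End Day 3 onwards belongs to the post-treatment windows.

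EOT failure, by contrast, has a lower day limit: "where the HCV RNA value must be collected on or after Study Drug Day 36 and study drug duration \geq 36 days".

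Protocol 8.1.2.2 defines the endpoint "among subjects who completed treatment as planned with HCV RNA $< \text{LLOQ}$ at the end of treatment" and sets no sample window for that condition.

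SAP 5.1.2 describes the sensitivity population as ITT "modified to exclude subjects who did not achieve SVR₁₂ for reasons other than virologic failure (mITT-VF").

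**The concern.** The protocol's condition concerns viral status when treatment ends. The SAP can answer it with a sample taken four weeks earlier while ignoring one taken a few days after the last dose. It is also inconsistent with itself: a value before Day 36 is too early to establish EOT failure, yet early enough to rule out relapse.

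The result is a gap between categories. A child who completes treatment, is shown to be suppressed just after the last dose and then has confirmed viraemia fits neither on-treatment failure, nor relapse, nor re-infection. Relapse is a named secondary endpoint, and very few failures are expected, so the coding of one child matters.

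**Working it through.** The documents state no figure on this point to reproduce. The check applies the rules to a constructed record and then looks at size.

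**1. How the pattern arises.** Protocol Appendix C (footnote b) gives the separate Week 8 visit only to 12- and 16-week subjects. An 8-week subject is therefore sampled on treatment at Weeks 2, 4 and 8 (EOT). No missed visit is needed. SAP 10.1 accepts 52 days as completion, and the nominal Week 8 day is 56. A last dose on Day 52 or 53 with a visit on Day 56 puts the EOT sample on End Day 56 − 52 = 4 or 56 − 53 = 3.

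**2. A record run through SAP 10.1.** 8-week subject, last dose Day 56. Week 2 = 300 IU/mL; Week 4 (Day 28) = 20; EOT sample on End Day 3 below LLOQ; post-treatment End Day 28 = 500,000; End Day 84 = 800,000.

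- Final Treatment value: 20 IU/mL, from Day 28.
- Breakthrough: no. There is no on-treatment rise of more than 1 log10 from nadir, and no value of 100 or more after suppression.
- EOT failure: no. The value predates Day 36.
- Re-infection and Relapse12: barred, because 20 is at or above the LLOQ of 15. Relapse_overall is barred for the same reason.
- Premature discontinuation: no (56 days is at least 52). Missing SVR12 data: no (End Day 84 lies within 57 to 126).
- Result: category 6, Other.

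**3. Controls.**

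| Change to the record | Result |
|---|---|
| EOT drawn on Day 56, below LLOQ | Relapse12 |
| Week 4 detected but below 15, EOT missing | Relapse12 |
| Week 4 sample drawn on Day 36 (= 20), EOT missing | EOT failure |
| 12-week subject, Week 8 below LLOQ, EOT missing | Relapse12 |
| 12-week subject, Week 8 = 20, EOT missing | EOT failure |
| 12-week subject, Week 8 and EOT both missing | Other |
| EOT missing and no SVR12-window sample | Missing follow-up data |

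**4. Effect of one case.** Assume that this child is the only non-responder. Intervals are 95% Wilson.

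| n | Quantity | As written | Scored as relapse |
|---|---|---|---|
| 22 (one Part 2 age group, Protocol 5.5.3) | mITT-VF SVR12 | 21/21 = 100% (84.5–100) | 21/22 = 95.5% (78.2–99.2) |
| 22 | Relapse | 0/21 = 0% (0–15.5) | 1/22 = 4.5% (0.8–21.8) |
| 125 | mITT-VF SVR12 | 124/124 = 100% (97.0–100) | 124/125 = 99.2% (95.6–99.9) |

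**5. How often.** Protocol 3.0 reports 22 adult virologic failures after removing one re-infection, among 2,256 treatment-naïve or TE-PRS subjects. Expected failures here: 125 × 22/2,256 = 1.2.

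The documents do not give the share of late or missing EOT samples, or the share quantifiable at Week 4. Assume 5–20% and 5–25%, independent of each other and of outcome.

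- Children with the sampling pattern: 125 × 0.05 × 0.05 = 0.3 to 125 × 0.20 × 0.25 = 6.
- Expected misclassified failures: 1.2 × 0.0025 = 0.003 to 1.2 × 0.05 = 0.06. At 10% and 15% this is 1.2 × 0.015 = about 0.02; if slow responders failed ten times as often, about 0.2.

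These figures err high for the late-sample case. They use all 125 children instead of the 8-week subjects, they include missing as well as late samples, and the 1.2 covers all virologic failures.

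**The case against.** **The SAP may already rescue the case.** SAP 10.1 says that a subject whose last available post-treatment value is at or above LLOQ counts as a relapse. By its own explanation, however, that sentence waives confirmation; it does not say that it waives the Final Treatment Visit condition. If it was meant to, the SAP should say so. SAP 6.3 admits a local laboratory value where the central one is missing, which closes the gap only if such a value exists.

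**Nothing is hidden.** This stands in part. The child remains an SVR12 non-responder in ITT and is still sequenced if HCV RNA reaches 1,000 IU/mL, as non-PVF. The case appears in the listings of non-responders (10.3.2), mITT-VF exclusions (10.5) and relapse-denominator exclusions (10.7). Listings disclose the case but do not correct the rate.

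**With EOT wholly missing, Other is defensible.** This stands. If the last on-treatment value is quantifiable and no later value below LLOQ precedes the viraemia, the suppression that the protocol requires was never shown, and relapse cannot be told from non-suppression. A reader might infer that every missing EOT sample produces the same error; the protocol's own condition does not support that.

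**The size is small.** This also stands. A reader might take the 0.3 to 6 children above as lost relapses. They are children with the sampling pattern, most of whom would be expected to be cured.

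**Conclusion.** The gap is real but narrow. It needs an 8-week completer, an EOT sample on End Day 3 or later that is below LLOQ, a Week 4 value of at least 15 IU/mL, and later confirmed viraemia with data in the SVR12 window. Such a child is coded Other. The child leaves the relapse numerator and denominator, mITT-VF and PVF and, if in Cohort 1, the mITT-VF polymorphism comparisons of SAP 10.8.1. Children with the same pattern who stay cured also drop out of the relapse denominator.

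Three stronger readings are not supported. The ITT SVR12 rate is not inflated. A result reported as detected but below 15 IU/mL does not trigger the problem. Subjects on 12 or 16 weeks are largely protected by their Week 8 sample, which falls after Day 36.

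The expected number of misclassified relapses is well below one under the assumptions shown, and the true frequency cannot be computed from the documents. The case for a change is that the rule gives a wrong classification, that one child could be most of an expected count of about 1.2, and that the repair costs almost nothing.

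**What to change.** In the Relapse12, Relapse_overall and re-infection definitions, for treatment completers without on-treatment virologic failure (breakthrough or EOT failure), state the condition as follows: HCV RNA below LLOQ at the Final Treatment Visit or, if no sample was collected from Study Day 36 through Study Drug End Day 2, below LLOQ at the first post-treatment value, before any quantifiable one. Use the same condition for the relapse denominator.

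The exclusion of on-treatment failure is needed. A looser rule accepting any later value below LLOQ would let a child with EOT = 20 IU/mL on Day 56, a suppressed post-treatment Week 4 value and later viraemia count as both EOT failure and relapse.

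Add that the sentence on the last available post-treatment value waives confirmation only. Report separately the completers who have no EOT sample and no value below LLOQ before the first quantifiable post-treatment value.

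The cost is a short edit to SAP 10.1 and one programming condition. The relapse percentage may become slightly less favourable.

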6.3 Missing Data Imputation

Missing Data Imputation for SVR

HCV RNA values will be selected for analysis based on the analysis windows defined in Section 6.2.

For analyses of SVR, subjects' missing visit values will have backward imputation applied, if possible. For backward imputation, if the nearest HCV RNA value after the SVR window is unquantifiable or undetectable, then it will be used to impute the HCV RNA value in the SVR window. If a subject is missing an HCV RNA value within the appropriate SVR window after performing backward imputation, then this value will be imputed with an HCV RNA value from a local laboratory if present; otherwise, the HCV RNA value will be missing. Subjects with missing HCV RNA data in the analysis window, after imputations, will be imputed as a failure.

Regardless of the imputation method described above, if a subject starts another treatment for HCV, then all HCV RNA values for this subject measured on or after the start date of the new HCV treatment will be excluded from analyses. The subject will be considered a failure for summaries of viral response at all time points after the start of the new HCV treatment.

Missing Data Imputation for Virologic Failure

If HCV RNA values from the central laboratory are missing but a local laboratory value is present in the appropriate time period, then the local laboratory value will be used to assess post-treatment relapse and on-treatment virologic failure.

Missing Data Imputation for PRO Questionnaires

The handling of missing data for patient reported outcomes (PROs) will be as follows. If a respondent answers at least 50% of the items in a multi-item scale of the PedsQL, the missing items will be imputed with the average score of the answered items in the same scale. In cases where the respondent did not answer at least 50% of the items, the score for that dimension will be considered missing.

Regardless of the imputation method described above, if a subject starts another treatment for HCV, then all PRO data for this subject measured on or after the start date of the new HCV treatment will be excluded from analyses.

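### A relapse first seen after a missed SVR12 window is coded as missing, then as other or missing, and the SAP contradicts itself on whether that child is a virologic failure

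*SAP*

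**What the plan says.** **Windows (SAP Table 4).** SVR12 is Study Drug End Days 57 to 126. SVR24 is Days 127 to 210.

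**Imputation (SAP 6.3).** Backward imputation works only from a negative value: "if the nearest HCV RNA value after the SVR window is unquantifiable or undetectable, then it will be used to impute" the window. If that fails, the value is "imputed with an HCV RNA value from a local laboratory if present". After that, "Subjects with missing HCV RNA data in the analysis window, after imputations, will be imputed as a failure".

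**Relapse definitions (SAP 10.1).** All three exclude reinfection.
- Relapse12 runs from end of treatment through the SVR12 window, in treatment completers who were below LLOQ at the Final Treatment Visit.
- Relapse24 is a confirmed quantifiable value in the SVR24 window "for a subject who achieved SVR₁₂ and has HCV RNA data available in the SVR₂₄ window".
- Relapse_overall has the same entry conditions as Relapse12 but runs to the last post-treatment measurement. *Virologic failure* is built on it.
- On the denominator: "Only subjects who have at least one post-treatment HCV RNA value will be included in analyses of relapse".
- A quantifiable last available post-treatment value counts as relapse without confirmation.

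**Non-response reasons (SAP 10.1).** The missing-data category for SVR12 is "defined as any subject who completed study drug without data in the SVR₁₂ window after applying the imputation rules" and meeting no higher-ranked reason. The SVR24 list works the same way and ends with *Other*.

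**Where these feed.** The secondary relapse endpoint is Relapse12 with a Wilson interval (SAP 10.4.2). Relapse_overall is counted by visit window (SAP 10.7). The mITT-VF population drops subjects who missed SVR12 for non-virologic reasons (SAP 5.1.2). The resistance section splits subjects into PVF and non-PVF and lists missing SVR12 data among the non-virologic reasons (SAP 10.8.1).

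**The concern.** The rules treat a missed SVR12 visit differently according to what the next sample shows. If it is negative, it is carried back and can make the child an SVR12 responder. If it is positive, it is not used to explain the failure, and the reason recorded is missing data even though the database holds a documented relapse.

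Two things are at stake. The reason tables are meant to tell a reader why children failed, and here they would give the wrong reason. And because the reason label conflicts with the SAP's own definition of virologic failure, two programmers following the text could place the same child in different analysis populations. That affects the mITT-VF sensitivity analysis (SAP 10.5), the PVF and non-PVF resistance summaries and, for an adolescent, the Cohort 1 comparisons of SVR12 by baseline polymorphism, which use mITT-VF and rest on very few failures.

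**Working it through.** The documents state no figure for this point, so there is nothing to reproduce. The check applies the rules to visit patterns and then sizes one affected child.

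**Step 1. Apply the rules.** Every child below completed treatment, was below LLOQ at the Final Treatment Visit and was not reinfected. PT = post-treatment; neg = below LLOQ; pos = at or above LLOQ.

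| Pattern | Relapse12 | Relapse24 | SVR12 reason | SVR24 reason | Relapse_overall |
|---|---|---|---|---|---|
| A. PT Wk 4 neg, SVR12 window empty, Wk 24 and 36 pos | No | No | Missing | Other | Yes |
| B. As A, but Wk 24 is the last value | No | No | Missing | Other | Yes |
| G. As A, with Wk 4 also missed | No | No | Missing | Other | Yes |
| C. Wk 4 neg, SVR12 and SVR24 windows empty, Wk 36 and 48 pos | No | No | Missing | Missing | Yes |
| D. Wk 4 pos, SVR12 window empty, Wk 24 and 36 pos | Yes | No | Relapse12 | Relapse12 | Yes |
| E. Wk 4 neg, SVR12 window empty, Day 140 neg, Day 200 and Wk 36 pos | No | Yes | SVR12 achieved by imputation | Relapse24 | Yes |
| H. As A, with a negative local value in the SVR12 window | No | Yes | SVR12 achieved | Relapse24 | Yes |

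Pattern A in words: the positive Week 24 value cannot be carried back, so the empty window is imputed as failure. Relapse12 closed at Day 126. Relapse24 needs SVR12, which was not achieved. Missing data is the first SVR12 reason that fits. At SVR24 the window holds data, so only *Other* is left. The later sample puts the child in the relapse denominator, where the Relapse12 outcome is a non-event.

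Pattern B reads the last-value rule as waiving confirmation only. Pattern D dates relapse by the first value of the confirmed pair.

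**Step 2. Set the population rules side by side for patterns A, B, C and G.**
- SAP 10.1: Relapse_overall is met, so the child is a virologic failure. By that route the child belongs in PVF and stays in mITT-VF as an SVR12 failure.
- SAP 10.8.1: the assigned SVR12 reason is missing data, listed there as non-virologic. By that route the child is non-PVF and, under SAP 5.1.2, leaves mITT-VF.

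**Step 3. Size of one affected child.** Inputs: about 22 children per Part 2 age group on the final dose (Protocol 5.5.3), about 125 overall (Protocol 8.2), Wilson 95% intervals with z² = 3.8415, and nobody else failing.

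Wilson interval = [p + z²/2n ± z√(p(1−p)/n + z²/4n²)] / (1 + z²/n). For x = 0 the upper limit is z²/(n + z²); for x = n the lower limit is n/(n + z²).

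- mITT-VF SVR12 in the age group, child excluded: 21/21 = 100%, lower limit 21/24.8415 = 84.5%.
- Child kept: 21/22 = 95.5%, interval 78.2% to 99.2%.
- Relapse in the age group: Relapse12 is 0/22, upper limit 3.8415/25.8415 = 14.9%; Relapse_overall is 1/22 = 4.5% (0.8% to 21.8%).
- Relapse overall: Relapse12 is 0/125, upper limit 3.8415/128.8415 = 3.0%; Relapse_overall is 1/125 = 0.8% (0.1% to 4.4%).

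**The case against.** A reader might infer that the plan loses the relapse, or that the gap flatters the main efficacy result. The documents do not support either. The child is imputed as an SVR12 failure, so the SVR12 rate is the same on any reading. The child stays in both non-response tables with the wrong reason, and Relapse_overall counts the child by window with the subject number (SAP 10.7).

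It is also tempting to call Relapse12 and Relapse24 misdefined. Both have a basis in the protocol. Protocol 8.1.2.2 limits the secondary relapse endpoint to 12 weeks after the last dose, and Protocol 8.1.2.3 lists relapse after achieving SVR12 as an additional endpoint. With no sample in Days 57 to 126, the data cannot show that viraemia returned within the Relapse12 period. Forcing the child into either definition would change a protocol-aligned endpoint.

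Nor does every missed SVR12 visit lead here. Patterns D, E and H are handled properly, and *Other* at SVR24 does not follow when that window is also empty. Read literally, the last-value rule would call some of these children relapses, although its wording suggests that it only waives confirmation. Nothing in the documents shows how often the pattern will occur or that children who miss the visit are more likely to relapse, and no efficacy endpoint is tested (SAP 10.2).

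On mITT-VF, one can fairly say that the defined term governs and the child stays in. That may be the better reading. It does not remove the conflict, because Section 10.8.1 names missing SVR12 data as non-virologic and refers to the same reason list. What stands is the mislabelled reason and the contradictory membership.

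**Conclusion.** The point holds, with limits. For a treatment completer with no quantifiable value by Day 126, an empty SVR12 window with no local value, and later viraemia that is confirmed or last available and not a reinfection, the SAP gives a wrong reason for SVR12 failure. It gives an uninformative or wrong reason for SVR24 failure, and contradictory rules for mITT-VF and PVF.

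Relapse_overall rescues the count but not a rate: SAP 10.7 specifies a count by window and listings, with no percentage or interval for Relapse_overall. The only planned relapse rate in the SAP is Relapse12, where this child is a non-event.

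The size is one child's worth per occurrence: 21/21 against 21/22 in an age group of 22, on the assumption that all others respond. The frequency is unknown and probably low. The change is worth making because the conflict can be settled now, before an actual case makes the choice of reading look driven by the result.

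**What to change.** Leave Relapse12 and the protocol endpoint of relapse after achieving SVR12 as they are. Amend the SAP as follows.

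1. **Reason lists (10.1).** Add to both the SVR12 and SVR24 lists a category *relapse first detected after a missed SVR12 window*: no value in the SVR12 window after imputation, and Relapse_overall met (treatment completed, confirmed or last available value at or above LLOQ, reinfection excluded) but neither Relapse12 nor Relapse24. Rank it after reinfection, Relapse12 and Relapse24, and before missing data and *Other*.
2. **Membership (5.1.2 and 10.8.1).** State that these subjects are virologic failures: kept in mITT-VF as SVR12 failures, assigned to PVF, and taken out of the missing-SVR12-data group.
3. **Last-value rule (10.1).** State which relapse endpoint or endpoints it serves, and whether it does more than waive confirmation.
4. **Reporting (10.7).** Give the Relapse_overall rate with a Wilson 95% interval, by age group and overall, beside the Relapse12 rate.

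The cost is one extra category, one extra rate and a few sentences, with no new data. The reported figures may be slightly less favourable.
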